## Statistical Analysis Plan

---

### 3.2 Procedures for recording and reporting outcomes

CRFs will be used to collect data from study entry. Two participant identifiers (trial number allocated at consent and initials) will be used on all CRFs. Data will be recorded by electronic data capture (EDC). Prime responsibility for the complete collection of data for each centre will reside with the local Principal Investigator but may be delegated (for example to a research nurse). Overall responsibility for collating data from all centres will reside with the Trial Manager.

### 3.3 SAE Review

As part of pharmacovigilance procedures, all blinded SAEs will be reviewed by the Chief Investigators in real-time.

### 3.4 Other assessments

None.

### 3.5 Trial Data Management and Verification

Quality control of data entered and data cleaning will be performed by the trial data manager and will be detailed in the Data Management Plan (FRM4727). This will include performing range, data completeness and consistency checks. Once this stage is finished, the trial dataset will be declared frozen and exported from the MACRO database for final data review and validation checks by a statistician, who will raise data queries with the trial manager or data manager. Once the trial statistician, data manager, and trial manager are satisfied that all queries have been resolved, the database will be locked. The locked database will be exported to the Statistical Master File and then imported into SAS and used for final analysis.

## 4. Detailed Analysis Plan

### 4.1 Interim analysis

Owing to the need to establish both the efficacy and safety of anti-fibrinolytic therapy, the intention is that TREATT will not stop randomising participants if anti-fibrinolytic therapy appears to show effectiveness in an interim analysis. This is because the trial will need to collect additional information on safety endpoints. This is judged important due to the low power the trial has to detect increased rates of thromboembolic events. Because TXA is currently being used off-label in thrombocytopenic participants, it is similarly judged important that any deleterious effect of anti-fibrinolytic therapy with respect to bleeding in thrombocytopenic participants be documented at a level that would be clinically and statistically credible. The Data Monitoring Committee will have overall oversight and can recommend terminating the trial early for these or any other safety concerns.

An interim analysis will be performed after 300 participants have been in the trial for 30 days. A summary of SAEs, UARs, thrombotic events, veno-occlusive disease and death, by treatment arm, will be provided to the Data Monitoring Committee. This summary will be performed by the independent statistician, and will remain inaccessible to the trial statistician, to ensure the trial statistician remains blinded. The population used for safety analyses will be all participants who receive any amount of trial treatment, using data gathered from first administration of trial treatment until up to 120 days after first administration of trial treatment. The population used

## Statistical Analysis Plan

---

for safety analyses of thrombotic events will be all participants who receive any amount of trial treatment, using data gathered from time of consent until 120 days after first administration of trial treatment.

In addition, a multivariate test for heterogeneity of UK and Australian baseline participant characteristics will be performed by the trial statistician. The population used for this analysis will be a modified intention to treat population including all eligible randomised participants whose platelet count falls to  $30 \times 10^9/L$  or below. Sex, diagnosis (acute leukaemia or not) and treatment plan (autograft or not) will be analysed as binary outcomes. The normal approximation to the binomial will be applied for each binary variable and sex, diagnosis (acute leukaemia or not), treatment plan (autograft or not) and haemoglobin at randomisation will be compared using Hotelling's T-squared test, as long as the following criteria are fulfilled: (i) the estimated proportions are not close to the [0, 1] boundaries; (ii) the number of participants in each binary outcome category is  $> 5$ ; (iii) for each binary variable, 3 standard deviations above and below the expected proportion is within the range [0, 1]. If not all the criteria are fulfilled, an alternative test will be considered: a logistic regression of participant country (UK or not) on sex, diagnosis (acute leukaemia or not), treatment plan (autograft or not) and haemoglobin at randomisation will be performed and the concordance statistic and its 95% confidence interval will be calculated. A confidence interval that does not include 0.5 would indicate evidence of a difference between UK and Australian participants. A summary of the multivariate test will be provided to the Data Monitoring Committee. Only strong evidence of a difference between UK and Australian participants will be considered as evidence of heterogeneity. If evidence of heterogeneity between UK and Australian participants is identified in the interim analysis, subgroup analysis by country of participant will be performed for the primary outcome in the main analysis.

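### The fallback test for UK/Australia differences compares an in-sample c-statistic with 0.5, so when it is used it indicates a difference in roughly 30–45% of homogeneous trials

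*SAP*

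**What the plan says.** SAP section 4.1 sets the timing: "An interim analysis will be performed after 300 participants have been in the trial for 30 days". Apart from the safety summary, the trial statistician compares UK and Australian participants on sex, acute leukaemia, autograft and haemoglobin at randomisation. Hotelling's T-squared is the main method, subject to three criteria for the normal approximation. Protocol section 11.4 names only that method.

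The SAP adds a fallback: "If not all the criteria are fulfilled, an alternative test will be considered". It consists of "a logistic regression of participant country (UK or not) on sex, diagnosis (acute leukaemia or not), treatment plan (autograft or not) and haemoglobin" at randomisation, from which "the concordance statistic and its 95% confidence interval will be calculated". The decision rule is "A confidence interval that does not include 0.5 would indicate evidence of a difference between UK and Australian participants".

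A filter follows: "Only strong evidence of a difference between UK and Australian participants will be considered as evidence of heterogeneity". Strong is not given a number. If heterogeneity is accepted, "subgroup analysis by country of participant will be performed for the primary outcome in the main analysis".

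**The concern.** A confidence interval can be used as a test only if it is compared with the value the statistic takes when nothing is going on. For a c-statistic from a model fitted and scored on the same data, that value is not 0.5. The fit chooses the sign and size of each coefficient so as to separate the two countries in the sample at hand. Chance differences in sex, diagnosis, treatment plan and haemoglobin are therefore all turned in the direction that raises the c-statistic. The SAP mentions nothing that would undo this, so the in-sample reading is the natural one.

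At stake is the decision to run the country subgroup analysis of the primary outcome. The plan presents that decision as resting on strong evidence, but on the fallback route the evidence would come from a test with a much higher error rate than its 95% label suggests.

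**Working it through.** **The plan's own figure.** The SAP gives no error rate for this rule. The benchmark is the 5% implied by a 95% interval.

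**Inputs from the documents.** About 300 participants at the interim; four covariates (three binary, one continuous), hence 4 degrees of freedom; a 95% interval compared with 0.5.

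**Assumed inputs (not in the documents).** UK share 50–95%; male 60%; acute leukaemia 50–95%; autograft 2–30%; independent covariates and normal haemoglobin; a DeLong standard error with a Wald interval.

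**Method.** Country was simulated as unrelated to every covariate. In each of 1,500 to 4,000 trials per setting the logistic model was fitted, and the in-sample c-statistic *c* was computed with its standard error. A false positive was counted when *c* − 1.96 × SE > 0.5. At 1,500 trials and a rate near 35%, the Monte Carlo standard error is √(0.35 × 0.65 / 1500) = 0.012.

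**Calibration.** Over all simulated trials, Hotelling's test rejects in about 4–6%. The 4-df likelihood-ratio test of the fallback model rejects in about 4–7%, or 2–2.5% in the sparsest settings. The data are therefore null, and the excess below belongs to the c-statistic rule.

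**Null centre.** The mean in-sample c-statistic is about 0.55–0.64.

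**False positives over all trials.** With common covariates (60/50/30%) the rate is 40–46%, or 39–42% with a logit-scale interval. With sparse covariates, where the fallback is more likely to be needed, it is about 28–41%.

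**False positives given that the criteria fail.** Failure was taken as a category count of 5 or fewer, or p ± 3 SE outside [0, 1], in either country. Selected settings:

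| UK share | Male / leukaemia / autograft | Criteria fail | CI excludes 0.5, given failure | LR test rejects, given failure |
|---|---|---|---|---|
| 60% | 60/50/3% | 100% | 33.7% | 6.0% |
| 75% | 60/50/8% | 86.2% | 38.8% | 4.0% |
| 75% | 60/95/3% | 100% | 29.0% | 4.5% |
| 85% | 60/50/15% | 65.9% | 43.1% | 4.6% |
| 95% | 60/50/30% | 88.1% | 45.4% | 6.4% |
| 95% | 60/95/3% | 100% | 36.3% | 2.1% |

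Where failure is common (more than 60% of trials) the range is 29–45%, which is about 6 to 9 times nominal (30/5 = 6; 45/5 = 9). Where failure occurs in only about 15–40% of trials the rate is 45–65%. Part of that is selection, because a chance imbalance helps to trip the criteria: the likelihood-ratio test also rises there, to 7–14%.

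**Reading strong evidence as a 99% interval.** The rate over all simulated trials is about 9–23%, against a nominal 1%.

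**Criterion (iii).** With the standard deviation of the sample proportion, p − 3√(p(1−p)/n) ≥ 0 gives p ≥ 9/(n+9), with the mirror limit near 1. That is 9/309 = 0.03 at n = 300 and 9/69 = 0.13 for a country with an assumed 60 participants. With the standard deviation of a single binary observation, p ≥ 3√(p(1−p)) gives p ≥ 0.9 while the upper limit gives p ≤ 0.1, so no proportion could pass.

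**The case against.** Hotelling's test is the main method and is well calibrated. The fallback applies only if the criteria fail, and even then it is only to be considered. The rates above therefore describe the fallback, not the interim procedure as a whole. That stands.

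A reader might infer that the rule declares heterogeneity at something close to a coin toss. The text does not say so. An interval excluding 0.5 indicates evidence of a difference, and a separate, stricter filter follows. The filter does soften the rule, but it has no number and no other statistic attached, and a 99% reading still leaves the error far above 1%.

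A reader might also infer from criterion (iii) that the fallback would always apply, since no proportion can pass if the standard deviation is that of one binary observation. The sentence opens with the normal approximation to the binomial and speaks of an expected proportion, so the standard deviation of the sample proportion is the natural meaning. The other reading would make the SAP's own main test unusable. This is a point of wording only.

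Lastly, the cost of a false trigger is small: one extra interaction analysis out of three listed subgroup variables, in a plan that openly makes no multiplicity adjustment (SAP section 4.2). The trigger uses baseline data only. The DMC receives a summary of the test, and interim Table 1 has a P value for each variable. All of this stands and limits the weight of the point, but it does not make the rule a valid test.

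**Conclusion.** The fallback rule is wrong as written, because 0.5 is not the null value of an in-sample c-statistic. When the fallback is used, it would indicate a difference in roughly 30–45% of trials with no true difference, or about 9–23% if strong evidence means a 99% interval. The exact rate depends on the country split, the covariate prevalences and the interval method, none of which the documents give. No assumed setting brought the 95% rule near 5%.

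The effect is confined to whether the country subgroup analysis of the primary outcome is run. The primary estimate and its type 1 error are not affected.

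**What to change.** In SAP section 4.1, replace the comparison of the interval with 0.5 by the overall 4-df likelihood-ratio test of the logistic regression already planned. This follows SAP section 4.2, which obtains regression p-values from differences in −2 × log-likelihood. If covariates are sparse, a permutation p-value for the c-statistic is preferable: permute the country labels, refit, and compare the observed c-statistic with the permuted ones.

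State one numerical threshold for strong evidence and apply it to both the fallback and Hotelling's test. The value is for the sponsor to choose in advance.

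In criterion (iii), say that the standard deviation is that of the sample proportion, and whether the criterion is checked within each country.

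If the interim has already been run with the fallback, report the likelihood-ratio p-value beside the c-statistic result.

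The cost is a few sentences in the SAP and one extra line of output. No new data are needed.

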Owing to the need to establish both the efficacy and safety of anti-fibrinolytic therapy, the intention is that TREATT will not stop randomising participants if anti-fibrinolytic therapy appears to show effectiveness in an interim analysis. This is because the trial will need to collect additional information on safety endpoints. This is judged important due to the low power the trial has to detect increased rates of thromboembolic events. Because TXA is currently being used off-label in thrombocytopenic patients, it is similarly judged important that any deleterious effect of anti-fibrinolytic therapy with respect to bleeding in thrombocytopenic patients be documented at a level that would be clinically and statistically credible. An interim analysis will be performed after 300 participants have been in the trial for 30 days. The independent DMC will have overall oversight and can recommend terminating the trial early for these or any other safety concerns. A summary of SAEs, UARs, thrombotic events and veno-occlusive disease will be provided to the DMC. In addition, a multivariate test for heterogeneity of UK and Australian baseline patient characteristics will be performed. Sex, diagnosis, (acute leukaemia or not), treatment plan (autograft or not) and haemoglobin at randomisation will be compared using Hotelling's T-squared test. Sample proportions for categorical variables will be considered to be approximately normally distributed for the purposes of the multivariate test. Only strong evidence of a difference between UK and Australian participants will be considered as evidence of heterogeneity. If evidence of heterogeneity between UK and Australian participants is identified in the interim analysis, subgroup analysis by country of participant will be performed for the primary outcome in the main analysis,

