### 4.6 Sub-Group analyses

Subgroup analyses will be performed for the primary outcome in the main analysis by including an interaction term. Analysis will be performed using the same methods as for the primary outcome, except a covariate and treatment-covariate interaction will be included in the model for each of the following variables in turn:

- Country of participant (UK vs. Australia), if evidence of heterogeneity between UK and Australian participants is identified in the interim analysis
- Platelet count at consent ( $\leq 30 \times 10^9/L$  vs.  $> 30 \times 10^9/L$ )

Treatment compliance during first 30 days of the trial (participant decided to stop taking trial treatment vs. participant did not decide to stop taking trial treatment). Although participants may decide to stop taking trial treatment for many reasons, the main reason is thought to be an unwillingness to take the large, over-encapsulated oral trial treatment. The over-encapsulated oral trial treatment is to be replaced with smaller tablets in the UK and Australia. Therefore, an additional analysis of treatment compliance will be performed using four mutually-exclusive categories: participant decided to stop taking trial treatment during the period of over-encapsulated oral treatment; participant decided to stop taking trial treatment during the period of oral treatment as tablets; participant did not decide to stop taking trial treatment during the period of over-encapsulated oral treatment; participant did not decide to stop taking trial treatment during the period of oral treatment as tablets. The number of UK participants who discontinued IV trial treatment during the period in September 2018 when oral treatment was unavailable will be described by arm.

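### The country-by-treatment analysis is run only if UK and Australian baseline characteristics differ at the interim, which does not test whether the treatment effect differs by country

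*SAP*

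**What the plan says.** Protocol section 11.4 states that at the interim "a multivariate test for heterogeneity of UK and Australian baseline patient characteristics will be performed". SAP section 4.1 repeats this, assigns it to the trial statistician, and times the interim: "An interim analysis will be performed after 300 participants have been in the trial for 30 days". The variables are sex, acute leukaemia or not, autograft or not, and haemoglobin at randomisation.

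The SAP gives two routes to a decision:

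- **Main route.** The four variables, ending with "haemoglobin at randomisation will be compared using Hotelling's T-squared test, as long as the following criteria are fulfilled". The criteria concern the normal approximation for the binary variables.
- **Fallback.** If the criteria fail, country is regressed on the same four variables and the concordance statistic is examined: "A confidence interval that does not include 0.5 would indicate evidence of a difference between UK and Australian participants".

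The general standard is "Only strong evidence of a difference between UK and Australian participants will be considered as evidence of heterogeneity". No numerical threshold is attached to it. The same section then states the consequence: "If evidence of heterogeneity between UK and Australian participants is identified in the interim analysis, subgroup analysis by country of participant will be performed".

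SAP section 4.6 carries the condition into the subgroup list: "Country of participant (UK vs. Australia), if evidence of heterogeneity between UK and Australian participants is identified in the interim analysis". It also appears in SAP section 2.3, the Protocol synopsis, and Protocol sections 7.3 and 11.5.3. The country table in SAP section 5.8 is produced only if the condition is met. Once it is met, the effect difference is examined with a treatment-by-country interaction in the primary model. The platelet-count and compliance subgroups use the same interaction method with no precondition.

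**The concern.** The country subgroup asks whether the effect of tranexamic acid on death or grade 2+ bleeding differs between the UK and Australia. The condition asks whether the two countries enrolled similar patients. A difference in case mix need not mean a difference in effect, and similar case mix does not exclude one.

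The documents name country-level features that the four baseline variables would not reflect. Transfusion practice refers to different national guidelines, and platelet type and dose are left open (Protocol 6.4.1 and 6.4.2). SAP section 4.6 also describes a period in September 2018 when oral treatment was unavailable and counts the UK participants affected.

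What is at stake is whether a two-country trial reports its country comparison at all. If the condition is not met, neither the interaction nor the table appears in the planned output. The health economic evaluation uses UK participants only (Protocol 11.3.4 and 12.2), so consistency between the UK and pooled effects bears on another planned result.

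**Working it through.** **The plan's own sample size.** Inputs from SAP section 1.5.2: 43% and 32% event rates, two-sided 0.05, 80% power, log-rank test.

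- Hazard ratio = ln(0.68)/ln(0.57) = 0.686.
- Events = 4 × (1.96 + 0.842)² / (ln 0.686)² = 222 after rounding up.
- Mean event probability = (0.43 + 0.32)/2 = 0.375. Participants = 222/0.375 = 592, about 1% above the stated 586.
- 586 × 1.05 = 615.3, which gives 616.

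The plan's basis is therefore reproduced. The expected number of events in the analysis set is 586 × 0.375 = 220.

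**Power of the interaction if always fitted.** With share s of events in one country and 1:1 allocation, SE of the interaction log hazard ratio = sqrt(4/(220s) + 4/(220(1−s))). Power = Φ(|ln ratio|/SE − 1.96). The documents give no country split, so s is assumed.

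| Assumed Australian share | SE | Power, HR 0.5 vs 1.0 | Power, HR 0.686 vs 1.0 |
|---|---|---|---|
| 20% | 0.337 | 54% | 20% |
| 30% | 0.294 | 65% | 25% |
| 40% | 0.275 | 71% | 28% |

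For s = 30%: sqrt(4/66 + 4/154) = 0.294; 0.693/0.294 − 1.96 = 0.39 and Φ(0.39) = 65%; 0.377/0.294 − 1.96 = −0.68 and Φ(−0.68) = 25%.

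**How often the baseline test triggers the subgroup.** This was simulated for the first 300 participants. Assumptions not in the documents: Australian share 20-40%; 60% male; haemoglobin mean 85, SD 12; and, for identical case mix, 60% acute leukaemia and 20% autograft in both countries.

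- Identical case mix, Hotelling at p<0.05: 5.0-5.6%, whether or not the treatment effect differs. At p<0.01: 0.9-1.4%.
- Identical case mix, C-statistic fallback with a DeLong interval: about 40% (38-43% across simulations). The C-statistic of a model assessed on the data used to fit it is biased above 0.5.
- Differing case mix (assumed acute leukaemia 75% vs 55%, autograft 10% vs 25%) and no effect difference, Hotelling: 89-99% at p<0.05 and 72-94% at p<0.01.

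The trigger rate follows case mix and the choice of route. It does not respond to effect modification.

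**Combining the two.** With identical case mix, the baseline test and the interaction test are close to independent. At a 30% share and HR 0.5 vs 1.0, the chance of both triggering the subgroup and detecting the difference is 0.05 × 65% = 3% by Hotelling at p<0.05, and 0.40 × 65% = 26% by the fallback. For 0.686 vs 1.0 the figures are 0.05 × 25% = 1% and 0.40 × 25% = 10%. The unconditional figures are 65% and 25%.

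**The case against.** The strongest defence is that the rule is pre-specified, uses no arm or outcome data, and limits subgroup testing in a plan that makes no multiplicity adjustment (SAP 4.2). All of that is correct. A reader might infer that the rule biases the primary result or inflates its type I error; it does neither.

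Second, the variables are relevant to bleeding. Protocol section 1.2 reports more bleeding in acute leukaemia and less after autologous transplant, and section 6.4.2 links low haematocrit to bleeding risk. A reader might infer that the baseline test says nothing about country effects, and that goes too far. With a constant hazard ratio of 0.686, a control risk of 43% gives a reduction of 11 points. An assumed control risk of 30% gives 30 − 100 × (1 − 0.70^0.686) = 30 − 21.7 = 8.3 points. The SAP reports risk differences and numbers needed to treat, so this matters. It does not justify the condition, because the analysis being withheld tests a ratio of hazard ratios, and the documents do not say that these variables modify the effect.

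Third, several sources of country difference are controlled: a common bleeding tool with trained assessors and central algorithmic grading (Protocol 8.2.1 and 8.2.2), and common platelet and red-cell thresholds (6.4.1 and 6.4.2). This lowers the prior chance of a country effect but does not make baseline similarity a test for one. Different discharge practice by country would be conjecture; no section reports it.

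Fourth, an unconditional test would usually miss a difference of the planned size. That stands. It is a reason to present the estimate with its interval as descriptive, not a reason to withhold it.

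**Conclusion.** The concern holds and is minor to moderate. Whether the country comparison is made and tabulated depends on a test of a different question, on about 300 participants, against an unquantified standard.

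A reader might infer that the condition always cuts the chance of finding a country difference from about 65% to 3%. The documents do not support that as a general figure. It needs identical case mix, a large difference (0.5 vs 1.0), an assumed 30% share, and Hotelling's test at p<0.05, a level the plan never attaches to this decision. Under the fallback the trigger rate with identical case mix is about 40%, if its 95% interval excluding 0.5 counts as sufficient, which the SAP leaves open. If case mix differs materially, the subgroup will probably be run anyway. Nor is it right that the trial could never examine country: nothing forbids a labelled exploratory analysis, although it would lack pre-specified standing.

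All power figures rest on assumed country shares of 20-40% and the planned event total of 220.

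**What to change.** Remove the condition in SAP sections 2.3, 4.1, 4.6 and 5.8, and in the Protocol synopsis and sections 7.3, 11.4 and 11.5.3. Always fit the country-by-treatment interaction for the primary outcome, as already planned for platelet count at consent. Always produce the country table, adding the interaction estimate with its confidence interval to the p-value in the present shell, and label the result low-powered and descriptive. Keep the UK versus Australia baseline comparison as description only, with no decision attached. The undefined standard of evidence and the fallback then no longer need resolving.

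The cost is one more unadjusted subgroup test to interpret and a wording amendment to the protocol as well as the SAP. The model and table shell exist, no new data are needed, and the primary analysis does not change. If the interim comparison has already been made, the change can still be made cleanly, because that comparison uses neither arm nor outcome data.
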